3.9 Discontinuation of investigational product

Subjects may be discontinued from osimertinib in the following situations:

- Subject decision. The subject is at any time free to discontinue treatment, without prejudice to further treatment
- Adverse Event
- Severe non-compliance with the study protocol
- Progressive disease or no clinical benefits

Patients experiencing corneal ulceration or Interstitial Lung Disease (ILD) will not be permitted to restart study treatment.

3.9.1 Procedures for discontinuation of a subject from investigational product

At any time, subjects are free to discontinue investigational product or withdraw from the study (i.e., investigational product and assessments – see Section 0), without prejudice to further treatment. A subject that decides to discontinue investigational will always be asked about the reason(s) and the

presence of any adverse events. If possible, they will be seen and assessed by an Investigator(s). Adverse events will be followed up (See Section 0); and all study drugs should be returned by the subject. If a subject is withdrawn from study, see Section 0.

3.10 Criteria for withdrawal

3.10.1 Screen failures

Screening failures are patients who do not fulfil the eligibility criteria for the study, and therefore must not be treated in the study.

3.10.2 Withdrawal of the informed consent

Patients are free to withdraw from the study at any time (investigational product and assessments), without prejudice to further treatment. A patient who withdraws consent will always be asked about the reason(s) and the presence of any adverse events (AE). The investigator will follow up AEs outside of the clinical study. If a subject withdraws from participation in the study, then his/her enrolment code cannot be reused. Withdrawn subjects will be replaced.

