1.2 Rationale for study design, doses and control groups

This open-label, single-arm, non-randomized phase 2 study has been designed to evaluate the efficacy of AZD9291 80mg once daily in NSCLC patients with EGFR exon 20 insertion mutation who

failed to standard chemotherapy.

In the phase 1 dose escalation study of AZD9291 (D5160C00001, AURA1), once daily doses of 20, 40, 80, 160, and 240mg of AZD9291 were evaluated.⁵ Based on the totality of the safety, pharmacokinetic and preliminary efficacy data, 80 mg once daily was selected as the recommended phase II dose. Please refer to the AZD9291 IB for additional details. No dosage adjustment is required due to patient age, body weight, gender, ethnicity and smoking status.

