If the toxicity does not resolve to \leq CTCAE grade 2 after 3 weeks, then the patient should be withdrawn from the study and observed until resolution of the toxicity.

Table 4. Dose Interventions

Intervention	AZD9291 Dose
Starting Dose	80 mg daily
Reduced Dose	40 mg daily

On resolution of toxicity within 3 weeks:

If an event subsequently requires dose interruption, AZD9291 may restart at the same dose or the reduced dose, on resolution/improvement of the event at the discretion of the clinician.

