8.2 Sample size estimate

The primary endpoint of this study is to evaluate the proportion of patients who achieved an objective response as assessed by the investigator according to RECIST version 1.1. Up to 30 patients (withdrawal 10%) will be enrolled and dosed in order to obtain at least 27 evaluable patients according to Simon's minimax two-stage design as follows: objective response, $P_0=0.05$ and $P_1=0.20$; type 1 error 5%, power 80%, and confidence limit 95%; stage 1 (objective response $\geq 1/13$) plus stage 2 (objective response $\geq 4/27$). All data will be presented for the overall full analysis set, and also by cohorts defined by subtypes of EGFR exon 20 insertion mutations (C-helix vs. loop following C-helix). Descriptive statistics will be used for all variables, as appropriate. Continuous variables will be summarised by the number of observations, mean, standard deviation, median, minimum, and maximum. Categorical variables will be summarised by frequency counts and percentages for each category. OS and PFS will be summarized using Kaplan-Meier estimates of the median event time and quartiles together with their 95% confidence intervals.

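### Replacement of withdrawn subjects is not limited to undosed patients, and Sections 3.10.2, 8.2 and 8.3 do not agree on who forms the 13 and the 27; if withdrawal goes with non-response, two or three replacements take type I error past 5%

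*Combined protocol and SAP*

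**What the plan says.** Section 3.10.2 (withdrawal of consent): "Patients are free to withdraw from the study at any time (investigational product and assessments"; it closes with "Withdrawn subjects will be replaced". The rule has no condition on dosing, time on study or response.

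Section 8.2 (sample size): "Up to 30 patients (withdrawal 10%) will be enrolled and dosed in order to obtain at least 27 evaluable patients". The same section sets a Simon minimax two-stage design with P0 = 5% and P1 = 20%, "type 1 error 5%, power 80%, and confidence limit 95"%. The trial goes on if at least 1 of 13 respond and succeeds if at least 4 of 27 respond. Evaluable is not defined beyond the Synopsis remark that it means evaluable for the primary analysis. No cut-off is given for any number other than 27.

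Section 8.3 (analysis sets) places dosed patients with a baseline tumour assessment in the efficacy set. A dosed patient who later withdraws would therefore stay in that denominator.

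Two other places bear on who counts as withdrawn. The note to the flow chart in Section 1.4 requires patients who stop drug without progression to continue tumour assessments until progression. Section 6.7 says of toxicity unresolved after 3 weeks: "then the patient should be withdrawn from the study and observed until resolution of the toxicity".

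**The concern.** A Simon design fixes the number of treated patients at each stage. Its error rate holds only if membership of the 13 and the 27 does not depend on outcome. Section 1.2 describes "This open-label, single-arm, non-randomized phase 2 study", and the primary endpoint is investigator-assessed, so patient and investigator both know how the patient is doing when a withdrawal is decided.

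Scans are every 2 cycles (Section 5.1) and the first cycle is 4 weeks (Synopsis). A patient who leaves before about week 8 therefore has no scheduled response assessment. The population has progressed on chemotherapy and may have performance status 2 (Section 3.1), so leaving because of decline is plausible. Each such patient who is replaced gives up a non-responder's place to someone who may respond.

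Two things are at stake: the stated 5% type I error, and the early stop on which Section 1.3 relies to limit exposure. With success set at 4 responses, one extra response can change the conclusion.

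**Working it through.** **Inputs.** From Section 8.2: P0 = 0.05, P1 = 0.20, continue at ≥1/13, succeed at ≥4/27, at most 30 enrolled and dosed, 10% withdrawal. The share of withdrawals who are non-responders is not given. It is varied from unrelated to response up to every withdrawal being a non-responder.

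**Step 1: reproduce the design.** With n1 patients in stage 1, n in total, and response rate p,

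P(success) = Σ over x from 1 to n1 of P(X1 = x) × P(X2 ≥ 4 − x), where X1 ~ Bin(n1, p) and X2 ~ Bin(n − n1, p).

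For n1 = 13, n = 27, p = 0.05:

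| Stage 1 responses | P(X1) | P(enough in the next 14) | Product |
|---|---|---|---|
| 1 | 0.3512 | 0.0301 | 0.0106 |
| 2 | 0.1109 | 0.1530 | 0.0170 |
| 3 | 0.0214 | 0.5123 | 0.0110 |
| 4 or more | 0.0031 | 1 | 0.0031 |

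The sum is 0.0416. At p = 0.20 the same formula gives power 0.8011. A full search for the minimax design at these settings returns the plan's rule. The stated design is therefore correct, and 5% is its ceiling, not its attained value. The enrolment figure also follows: 27/0.90 = 30.

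**Step 2: replace dosed non-responders.** If k1 non-responders are replaced in stage 1 and k2 in stage 2, the responses counted are those among 13 + k1 and 27 + k1 + k2 treated patients, with the cut-offs still at 1 and 4. Type I error at p = 0.05:

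| Replacements | Split (k1, k2) and type I error |
|---|---|
| 0 | 0.0416 |
| 1 | (0,1) 0.0463; (1,0) 0.0470 |
| 2 | (0,2) 0.0512; (1,1) 0.0521; (2,0) 0.0528 |
| 3 | (0,3) 0.0563; (1,2) 0.0574; (2,1) 0.0582; (3,0) 0.0589 |

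Three is the most within 30 patients, since 30 − 27 = 3.

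**Step 3: make withdrawal a probability.** Let each non-responder withdraw with probability w and be replaced, up to 30 enrolled. Type I error is 0.0480 at w = 5%, 0.0532 at 10% and 0.0578 at 20%. It crosses 5% at about w = 6.7%. If withdrawal is unrelated to response, it stays at 0.0416 at every rate.

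**Step 4: early stop under P0.** The chance of no response in stage 1 is 0.95^13 = 0.513. With one stage 1 replacement it is 0.95^14 = 0.488, and with two 0.95^15 = 0.463.

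**Step 5: does Section 8.3 repair this?** Suppose withdrawn patients stay in the set, stage 1 stays at 13, the total grows and the cut-off stays at 4. Type I error is 0.0463 at n = 28, 0.0512 at n = 29 and 0.0563 at n = 30. Keeping them in the denominator does not by itself hold 5%.

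**The case against.** The strongest reply is that the effect is small and conditional. The attained error is 4.2%, so there is slack. One replaced non-responder leaves it under 5%, and withdrawal unrelated to response does nothing. The documents give no evidence on who withdraws. All of that stands, and it limits the size of the point.

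The reply continues that most patients who fail are not withdrawn under Section 3.10.2. Progression, lack of benefit and adverse events are grounds for stopping drug (Section 3.9), and those who stop without progression stay under assessment (Section 1.4). This also stands. A reader might infer that any dosed non-responder who stops is swapped, but the text supports that only for patients who leave both drug and assessments.

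A reader might likewise infer from Section 6.7 that toxicity failures are replaced. That section does not say so. The replacement sentence sits under withdrawal of consent, and Table 3 describes unresolved toxicity as permanent discontinuation of drug. What remains is that the wording of Sections 6.7 and 1.4 needs reconciling.

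A third tempting reading is that replacement has no cap. Five replacements (2 + 3) would give 7.0% and six (3 + 3) 7.7%, but these need 32 and 33 dosed patients. Section 8.2 says up to 30, and the three extra patients are most naturally the replacement allowance itself. The Synopsis also says approximately 30, so the limit could be firmer, but the larger figures lie outside the stated plan.

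Finally, Section 8.3 keeps dosed withdrawals in the reported rate and its confidence interval. That is true, and it helps the estimate. It does not say which patients the 1/13 and 4/27 rules apply to, and Section 8.2 ties those rules to evaluable patients. The gap remains.

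**Conclusion.** The point holds in a limited form. As written, the plan lets a dosed patient who leaves drug and assessments be replaced, and Sections 3.10.2, 8.2 and 8.3 do not agree on who forms the 13 and the 27. The 10% allowance in Section 8.2 is for patients already enrolled and dosed, so replacing dosed patients is within what the plan foresees.

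The size rests on two assumptions: that the replaced patients are non-responders, and that the cut-offs stay at 1 and 4. On those, the stated 5% is passed only with two or more replacements, and the worst case within 30 patients is 5.9%. The plan's own 10% allowance is enough to reach that range. The documents do not show that withdrawal will be linked to non-response, so a certain breach of 5% cannot be claimed. The excess is under one percentage point, but it is avoidable, and as the text stands a dosed patient's place can be decided after the outcome is known. The change should be made.

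**What to change.** - **Section 3.10.2.** Replace the closing sentence with: 'Subjects who withdraw before the first dose, or who have no baseline tumour assessment, will be replaced. Other dosed subjects will not be replaced.'
- **Section 8.2.** Define evaluable as membership of the Section 8.3 efficacy set. State that the 1/13 and 4/27 rules apply to the first 13 and first 27 such patients, and that a patient with no response recorded before withdrawal counts as a non-responder.
- **Section 8.2, allowance.** Reword the 30-patient figure to match. It now refers to patients enrolled and dosed; under this rule the extra places cover only subjects without a dose or a baseline tumour assessment. Because Section 5.1 requires baseline imaging before treatment, the second group should be nearly empty.
- **Sections 6.7 and 1.4.** Reconcile withdrawal from the study for unresolved toxicity with the continued tumour assessments required after stopping drug.

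With this, type I error returns to 4.2% and power to 80.1%, provided 20% is the response rate over all dosed patients.

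The edits are a few sentences, but they have a statistical cost. The reported response rate may be slightly lower. If 20% is instead the rate among assessed patients, and 5% or 10% of dosed patients withdraw unassessed, the effective rate is 0.95 × 0.20 = 0.19 or 0.90 × 0.20 = 0.18. The Step 1 formula then gives power of about 76% or 72%. The sponsor should state which population the 20% refers to and accept or plan for that loss.

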3.11 Discontinuation of the study

The study may be stopped if, in the judgment of sponsor, trial subjects are placed at undue risk because of clinically significant findings that:

- meet individual stopping criteria or are otherwise considered significant
- are assessed as causally related to study drug,
- are not considered to be consistent with continuation of the study

Regardless of the reason for termination, all data available for the subject at the time of discontinuation of follow-up must be recorded in the CRF. All reasons for discontinuation of treatment must be documented. In terminating the study, the Sponsor will ensure that adequate consideration is given to the protection of the subjects' interests.

4. Study plan and timing of procedures

Table 1 Study Plan detailing the procedures

Visit

Visit window

Days -28 to 0 for Visit 1

±0 day for Visit 2

±1 day for Visits 3 and 4

±5 days starting at Visit 5 1

Screening	2	3	4	5	6	7	8 (n)	30-day	follow-up
-----------	---	---	---	---	---	---	-------	--------	-----------

For details see Protocol Section

Week	0	2	4	8	12	16	20+		Section
------	---	---	---	---	----	----	-----	--	---------

Day	-	0	14	28	56	84	112	140+	-
-----	---	---	----	----	----	----	-----	------	---

Written informed consent (including tissue samples, pharmacogenetics) X

Demographics X

Physical examination, height, and weight X
X

Medical/surgical history X

Inclusion/exclusion criteria X

Archival tumor tissue X

12-lead ECG	X	X	X	X	X	X	X	X	X
-------------	---	---	---	---	---	---	---	---	---

Vital signs	X	X	X	X	X	X	X	X	X
-------------	---	---	---	---	---	---	---	---	---

AZD9291 dispense/return		X		X	X	X	X	X	X
-------------------------	--	---	--	---	---	---	---	---	---

Concomitant medication	X	X	X	X	X	X	X	X	X
------------------------	---	---	---	---	---	---	---	---	---

Adverse event review (AEs and SAEs)			X	X	X	X	X	X	X
X	X								

Blood samples for haematology and clinical chemistry			X	X	X	X	X	X	X
--	--	--	---	---	---	---	---	---	---

	X	X	X					
Urinalysis	X	X	X	X	X	X	X	X
Blood sampling for cfDNA			X			X		X

4.1 Enrolment/screening period

Procedures will be performed according to the Study Plan (Table 1). At screening, consenting subjects are assessed to ensure that they meet eligibility criteria (Sections 3.1 and 3.2). Subjects who do not meet these criteria must not be enrolled in the study. All subjects will be required to provide consent to supply a sample of their archival tumor samples for entry into this study. This consent is included in the main subject informed consent form.

4.2 Treatment period

Descriptions of the procedures for this period are included in the Study Plan (Table 1) with exceptions of the following specific requirements for the treatment period: Subjects will receive osimertinib 80mg once daily until disease progression, unacceptable toxicities, or no clinical benefits.

4.3 Follow-up period

Descriptions of the procedures for this period are included in the Study Plan (Table 1) with exceptions of the following specific requirements for the follow-up period: Patients will return to the clinic/hospital for follow-up assessments 30 days (± 7 days) after their last dose. If a patient discontinues AZD9291, they will also attend a study treatment discontinuation visit.

5. Study assessments

The investigator will ensure that data are recorded on the electronic Case Report Forms (eCRFs) as specified in the study protocol and in accordance with the instructions provided.

The investigator ensures the accuracy, completeness, and timeliness of the data recorded and of the provision of answers to data queries according to the sponsor agreement. The investigator will sign the completed eCRFs. A copy of the completed eCRFs will be archived at the study site.

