1.4 Study Design

This is a single-arm, non-randomized multicentre phase 2 study in NSCLC patients with EGFR exon 20 insertion mutation, whose disease has progressed on standard chemotherapy. Full details of the assessments conducted at each visits are shown in Table 1.

Figure 1 Study flow chart

(a) Patients will continue to receive osimertinib until objective disease progression (according to RECIST 1.1) or for as long as they are receiving clinical benefit in the opinion of the Investigator unless any of the criteria for treatment discontinuation are met first. Patients who discontinue study treatment for reasons other than disease progression must continue tumour assessments as per the protocol schedule until progression.

2. Study objectives

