2.2 Secondary objectives

Secondary Objectives Outcome Measure

To evaluate the safety and tolerability of osimertinib AEs/SAEs as defined by NCI CTCAE version 4.0

To evaluate progression-free survival (PFS) PFS as defined by RECIST version 1.1

To evaluate overall survival (OS)

To evaluate the efficacy based on subtypes of EGFR exon 20 insertion mutation

To evaluate PFS based on subtypes of EGFR exon 20 insertion mutation

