5.1 Efficacy assessments

RECIST 1.1 guidelines for measurable, non-measurable, target lesions (TLs) and non-target lesions (NTLs) and the objective tumour response criteria are present. Baseline CT or MRI assessments of chest and abdomen (including liver and adrenal glands) must be performed no more than 28 days before the start of study treatment, and ideally should be performed as close as possible to the start of study treatment. Additional imaging may be performed based on individual patient signs and symptoms. The methods of assessment used at baseline should be used at each subsequent follow-up assessment. Follow-up assessments should be performed every 2 cycles (\pm 7 days) after the start of treatment until objective disease progression as defined by RECIST 1.1. Any other sites at which new disease is suspected should also be appropriately imaged. If an unscheduled assessment is performed and the patient has not progressed, every attempt should be made to perform subsequent assessments at the scheduled visits whilst the patient remains on study treatment.

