6.3 Recording of adverse events

6.3.1 Time period for collection of adverse events

Adverse Events will be collected from time of signature of informed consent, enrolment throughout the treatment period and including the 30-day follow-up period. SAEs will be recorded from the time of informed consent.

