8.5.2 Analysis of the secondary variable(s)

PFS will be summarized using Kaplan-Meier estimates of the median time to progression. OS will be summarized using Kaplan-Meier estimates of the median time to death or censoring and quartiles together with their 95% confidence intervals.

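### Overall survival is a secondary endpoint, but the readable protocol plans no survival check after the 30-day visit for patients who stop at progression

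*Combined protocol and SAP*

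**What the plan says.** Section 2.2 lists OS among the secondary objectives. Section 8.2 gives the analysis: "OS and PFS will be summarized using Kaplan-Meier estimates of the median event time and quartiles together with their 95% confidence intervals". Section 8.5.2 words it differently: "OS will be summarized using Kaplan-Meier estimates of the median time to death or censoring and quartiles together with their 95% confidence intervals". Neither section says when OS starts or on what date a living patient is censored.

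Section 4.3 covers follow-up. It refers to Table 1, mentions a discontinuation visit, and adds: "Patients will return to the clinic/hospital for follow-up assessments 30 days (± 7 days) after their last dose". The visit columns of Table 1, as far as they can be read, also end at the 30-day follow-up.

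Three other provisions could extend contact:

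- **Tumour assessments.** Under Figure 1 in section 1.4: "Patients who discontinue study treatment for reasons other than disease progression must continue tumour assessments as per the protocol schedule until progression". Section 5.1 likewise runs scans "after the start of treatment until objective disease progression as defined by RECIST 1.1".
- **Adverse events.** Section 6.3.1 collects them "throughout the treatment period and including the 30-day follow-up period". Section 6.4 adds follow-up to resolution. Section 6.3.2 says that events still open at the last visit are followed clinically but no longer entered on the case report form.
- **Deaths.** Section 6.3.11 makes deaths reportable if they occur during the study or in the 30-day period. Section 9.3 ends the study at the last patient's last visit.

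**The concern.** Patients who stop because of progression are the ones whose later deaths largely determine OS, and they have no planned contact beyond about a month after last dose. Censoring them there is informative when they are at higher risk of death than the patients who stay under observation. Kaplan-Meier assumes that the two groups have the same risk. The study has one arm, so there is no control group in which the error could cancel. The gap lies in what is collected, and a later analysis plan cannot recover survival dates that nobody sought.

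The wording in section 8.5.2 adds to this. Time to death or censoring is not OS, because censoring is not an outcome.

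**Working it through.** **1. The plan's own figure.** The only sample-size figure is the Simon minimax design in section 8.2. With at least 1 response in 13, then at least 4 in 27, the exact type 1 error is Σ over x ≥ 1 of P(X₁ = x)·P(X₂ ≥ 4 − x) = 0.0416 at a response rate of 0.05. The power is 0.801 at 0.20, and 27/(1 − 0.10) = 30. The figures reproduce. They concern response only; OS has no target number of deaths.

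**2. Which contact could establish survival after the 30-day visit?**

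| Provision | Covers a patient who stopped at progression? |
|---|---|
| 4.3 visit | Only to 23–37 days after last dose (30 ± 7) |
| 1.4 and 5.1 scans | No: they end at progression |
| 6.3.1, 6.3.2 and 6.4 adverse events | 30 days or event resolution; not a survival check |
| 6.3.11 deaths | A duty to report, with no means of finding the death |
| 9.3 end of study | Sets no contact for patients who have left |

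**3. How many would die inside the window?** The protocol gives no survival figures, so every survival input from here on is assumed. With exponential survival after progression, P(death by d days) = 1 − 2^(−(d/30.44)/median). For d = 23 to 37 this is 5.7–8.9% with a 9-month median and 8.4–13.1% with a 6-month median. So 87–94% would be alive when contact ends.

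**4. One case worked by hand.** Assume a median of 3.5 months to progression or death, 10% of these first events being deaths, a 6-month median after progression, treatment stopping at progression, and status known for 1 month after that.

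- Monthly hazards: λ = 0.6931/3.5 = 0.1980 for the first event; μ = 0.6931/6 = 0.1155 for death after progression.
- True survival: S(t) = e^(−λt) + [0.9λ/(λ − μ)]·(e^(−μt) − e^(−λt)). At t = 10.4: 0.1275 + 2.160 × (0.3007 − 0.1275) = 0.502. The true median is about 10.4 months.
- From month 1 on, for each progression-free patient at risk there are r = 0.9λ(e^(λ−μ) − 1)/(λ − μ) = 0.186 patients who progressed within the past month and are alive. Kaplan-Meier therefore estimates a hazard of (0.1λ + μr)/(1 + r) = (0.0198 + 0.0215)/1.186 = 0.0348.
- ln 2/0.0348 = 19.9 months. The lower hazard in month 1 (cumulative 0.0276 instead of 0.0348) adds 0.2, giving about 20.1.
- Bias: 20.1 − 10.4 = about +9.7 months.

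With 20% of first events being deaths and a mean of 2 months' treatment beyond progression, simulation gives 11.1 against 9.5 months (+1.6).

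**5. Grid.** The inputs were: median to first event 2.5, 3.5 or 6 months; post-progression median 6 or 9 months; 10, 20 or 30% of first events deaths; mean treatment beyond progression 0, 1 or 2 months. That is 3 × 2 × 3 × 3 = 54 scenarios, with uniform accrual over 15 months, cut-off at month 24 and no later death found. In 27 patients:

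- Deaths recorded: 3.7–13.0, against 13.1–21.7 with survival follow-up (26–64% captured).
- Patients censored alive at their last visit before cut-off: 39–81%, or 0.39 × 27 = 10.5 to 0.81 × 27 = 21.9.
- Bias in the median: −0.3 to about +10 months. In 5 to 7 scenarios, depending on the random draws, the median is not reached.
- The bias exceeds +1 month, or the median is not reached, in 41 of 54. It is negative in 3. In those the hazard of death before progression (0.3 × 0.6931/2.5 = 0.083) is above that after it (0.6931/9 = 0.077).

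These counts describe the grid and are not probabilities.

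**6. If some later deaths surface.** Suppose deaths are found at random while patients not found to have died stay censored at their last visit. With a quarter found, the bias is −0.9 to +4.1 months; with half, −1.7 to +1.1. Found deaths enter as events, but survivors gain no extra time, which pulls the median down. If status at cut-off is known for a random 80% of patients, living or dead, the bias is at most +0.8 months; for 90%, at most +0.4.

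**The case against.** **Parts of the protocol cannot be read.** Section 4.3 hands its detail to Table 1, which is visibly incomplete in the available text: it has no row for tumour assessments although section 5.1 requires them. Figure 1 is not shown and the appendices are absent. A missing survival row in that table proves little. This stands as a limit on confidence. However, the readable visit columns stop at 30 days, and the note under Figure 1 mentions no survival contact.

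**Later deaths may be recorded anyway.** Read literally, section 6.3.11 makes a death before the study ends reportable even after the patient's own last visit. This also stands. A reader might infer that all such patients are certain to be censored at a month and that the reported median will be too long. The protocol does not say that later deaths go unrecorded; it only provides no way of finding them. Step 6 shows that the direction is unknown if half surface.

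**The interval may give warning.** A reader might also infer that the 95% interval hides the problem. In simulated trials of 27 patients over the same grid, the upper limit of the median was not reached in 55–96% of trials (1.5–78% with full follow-up). Coverage of the true median was 56–96%, with a median of 89% across scenarios. The interval often looks open-ended, and coverage is seriously poor only in the more extreme scenarios.

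**Weight.** OS is secondary and descriptive, with no test attached. That is correct and limits the importance of the point.

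**Conclusion.** The concern holds in conditional form. The readable text plans no way to establish survival status after the 30 ± 7 day visit for patients who stop at progression, and it states no OS origin or censoring date. If few or no later deaths are ascertained, the OS median tends to be too long or not reached: about 0 to +10 months of bias on the assumed grid. If about half surface by chance, the bias is roughly −2 to +1 months with no known direction.

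These sizes rest on exponential times and on assumed survival and accrual, so they show what is possible and do not forecast this trial's result. An unconditional claim that the OS median will be too long is not supported. Nothing here touches the primary response analysis or the sample size.

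**What to change.** - **Sections 4.3 and 9.3, and Table 1:** add periodic survival-status checks by telephone or chart after the 30-day visit, for patients who have not withdrawn consent, up to a fixed data cut-off. Add a vital-status sweep at cut-off that records living patients as well as deaths.
- **Section 6.3.11 and the eCRF:** record these later deaths for OS.
- **Section 8.5.2:** define OS from a stated origin (for example, first dose) to death from any cause, censored at the date last known alive, in place of the present wording.
- **If the complete Table 1 or Figure 1 already shows survival follow-up:** make section 4.3 match it.

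The cost is a few calls or chart checks per patient by existing staff for about 30 patients, one eCRF page, protocol wording, and possibly consent wording. The sample size does not change.
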